9.2.5 Pain

- The management of pain should be done according to severity and recommended drugs.

9.2.6 Hypercalcaemia prophylaxis

Patients with asymptomatic hypercalcaemia do not require immediate treatment if calcium remains < 12 mg/dL (3 mmol/L). However, the patient should be advised to avoid factors that can aggravate hypercalcaemia (such as thiazide diuretics, volume depletion, prolonged bed rest or inactivity, and a high calcium diet [> 1000 mg/day]).

Adequate hydration (at least 6 to 6 glasses of water per day) is recommended to minimise the risk of nephrolithiasis.

9.2.7 Prophylaxis for skin toxicity and alopecia

Guidelines for prophylaxis are detailed in Appendix A.

9.3 Dose-limiting toxicity during Phase 1

The following AEs or laboratory abnormalities, graded according to NCI-CTCAE version 4, are considered to be DLTs when occurring during the DLT evaluation period (Day 1 to Day 28 of Cycle 1, plus the assessments prior to drug administration on Cycle 2, Day 1 and the Investigator feels are possibly, probably, or definitely related to Debio 1347 excluding those that are clearly and incontrovertibly due to disease progression or extraneous causes.:

- Febrile neutropenia (ANC < 1.0 X 10⁹/L and fever ≥ 38.2°C [101° F])

- Grade 3 or higher neutropenia with infection.
- Grade 4 neutropenia persisting for more than 7 days.
- Grade 4 thrombocytopenia persisting for more than 7 days or Grade 3 thrombocytopenia requiring platelet transfusion.
- Grade 3 diarrhea, constipation, nausea, vomiting or skin toxicity that lasts longer than 72 hours despite optimal symptomatic therapy.
- Any Grade 4 diarrhea, constipation, nausea, vomiting or skin toxicity.
- Grade 3 or higher liver function tests (ALT, AST, γ GPT) and ALP unless as clarified below
- Grade 3 or higher non-hematologic toxicity including Hy's law: AST and/or ALT $> 3 \times$ ULN and bilirubin $> 2 \times$ ULN, and without initial findings of cholestasis (serum alkaline phosphatase (ALP) activity $< 2 \times$ ULN) and no other reason that could explain the combination of increased transaminases and serum total bilirubin, such as viral hepatitis A, B, or C, preexisting or acute liver disease (including preexisting liver metastases), or another drug capable of causing the observed injury.
- The following non-hematologic AEs are not considered DLTs:
 - a. Grade 3 electrolyte abnormalities lasting < 24 to 72 hours, is not clinically complicated, and resolves spontaneously or responds to conventional medical interventions; and \geq Grade 3 amylase or lipase that is not associated with symptoms or clinical manifestations of pancreatitis.
 - b. Grade 3 or higher of ALP clearly related to bone metastases evolution. The relationship should be discussed with the study Medical Monitor on a case by case basis.
- Hyperphosphataemia:
 - a. Serum Pi > 7.0 mg/dL for > 7 consecutive days despite phosphorus lowering therapy for at least 14 days.
 - b. Serum Pi > 9.0 mg/dL, despite phosphorus lowering therapy for at least 14 days.
 - c. Serum Pi > 10.0 mg/dL.
- Any treatment delay more than 7 days because of treatment-related AEs or laboratory abnormalities occurring during the DLT period.
- Any other life-threatening toxicity.
- Other AEs considered intolerable by the Investigator.
- Death not clearly due to the underlying disease or extraneous causes

Patients experiencing a DLT during the DLT period may continue treatment after treatment adjustments if there is a potential benefit from treatment.

9.4 Dose Modifications or Scheduling Delays

- This study will use the NCI Common Toxicity Criteria (CTC) AE version 4.0 for toxicity.
- Study treatment will be temporarily or permanently discontinued due to the occurrence of AEs as specified in Table 1 below, for both the phase 1 and 2 portions of this study.
- Additionally, non-treatment related or unexpected toxicities may require interruption of therapy at the discretion of the Investigator.

- Failure to recover to the specified levels following temporary discontinuation within 7 days in the phase 1b portion and 14 days in the phase 2 portion will result in permanent treatment discontinuation. The treating Investigator and the PI will discuss the case of any patient whose treatment has been delayed for more than 7 or 14 days, respectively, who they think may benefit from continued treatment, prior to resuming treatment.
- In addition, if Grade 2 or higher toxicity occurs, treatment may be temporarily discontinued at the discretion of the Investigator. The patients may resume at the same dose level when toxicity has resolved to Grade 1 or below or the baseline level if resolution is achieved within 7 days in the phase 1b part and 14 days in the phase 2 part.
- In the event the patient requires temporary treatment discontinuation, the Investigator may choose to increase the frequency of the assessments performed to weekly collections until resolution.
- Only in the phase 2 portion, one dose reduction can be undertaken except for dose level -1 (60mg). Patients resuming treatment following a temporary discontinuation can do so at their original dose level or at one lower dose level.
- Patients experiencing a DLT during the DLT period may continue treatment after dose adjustments if there is a potential benefit from treatment after discussion with the PI
- Patients will be permanently discontinued if reduction beyond <60mg/day is necessary in both phase 1 and phase 2 portions of the study
- Reduced doses may not be re-escalated.
- If a patient discontinues Debio 1347 purely due to toxicity, they can stay on study and continue to receive fulvestrant. The patient will be captured as coming off of Debio 1347 due to toxicity and report TTF.

Table 1: Dose Modifications and Delays during Phase 1 and Phase 2

Adverse Event	Grade	Action	
		Phase I part: DLT evaluation period only	Phase I part: non-DLT evaluation period Phase 2 portion
Febrile neutropenia, Neutropenia with infection	4	Permanent discontinuation	Permanent discontinuation
	3	Permanent discontinuation	Temporary discontinuation until recovery to Grade 0
Neutropenia	3, 4	Temporary discontinuation until recovery to Grade 2	Temporary discontinuation until recovery to Grade 2
Thrombocytopenia	4	Permanent discontinuation	Temporary discontinuation until recovery to Grade 1
	3	Temporary discontinuation until recovery to Grade 1 Permanent discontinuation if a platelet	If a platelet transfusion is required, temporary

Adverse Event	Grade	Action	
		transfusion is required	discontinuation until recovery to Grade 1
Diarrhea, constipation, nausea, vomiting	3,4	Permanent discontinuation, if not manageable by optimal symptomatic therapy	Temporary discontinuation until recovery to Grade 2, or baseline
Skin toxicity (See additional guidelines in 9.4.1)	3,4	Permanent discontinuation, if not manageable despite prophylaxis and optimal symptomatic therapy	Temporary discontinuation until recovery to Grade 2, or baseline
Hyperphosphataemia		Please use the treatment guidelines per 9.4.2	Please use the treatment guidelines per 9.4.3
Hypertension	4	Permanent discontinuation	Permanent discontinuation
	3	Permanent discontinuation	If uncontrolled, temporary discontinuation until control is achieved
Hepatotoxicity (AST, ALT, ALP, γ GTP increased)	4	Permanent discontinuation	Permanent discontinuation
	3	Temporary discontinuation, until recovery to Grade 2	Temporary discontinuation, until recovery to Grade 2
Other non-haemotoxicity (except for transient electrolyte abnormalities)	4	Permanent discontinuation	Permanent discontinuation
	3	Permanent discontinuation	Temporary discontinuation until recovery to Grade 1 or baseline
Recovery from above AEs		Permanent discontinuation, if failure to recover within 7 days, otherwise treatment at same dose level. Dose reduction during the DLT has to be discussed with the PI	Permanent discontinuation, if failure to recover within 14 days, otherwise retreatment at next lowest dose level

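### Section 9.4 gives overlapping recovery conditions for restarting Debio 1347 (Grade 1 or baseline in one bullet, Grade 2 in four Phase 2 rows of Table 1) and does not say which governs

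*Combined protocol and SAP*

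**What the plan says.** Section 9.4 first sends holds and stops to the table, for both phases: "Study treatment will be temporarily or permanently discontinued due to the occurrence of AEs as specified in Table 1 below". A later bullet sets the trigger for the permanent stop: "Failure to recover to the specified levels following temporary discontinuation within 7 days in the phase 1b portion and 14 days in the phase 2". The consequence it names is permanent discontinuation. The same bullet provides that the treating investigator and the PI discuss any patient delayed beyond the window who they think may still benefit, before treatment resumes.

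The next bullet adds a second route: "In addition, if Grade 2 or higher toxicity occurs, treatment may be temporarily discontinued at the discretion of the Investigator". It continues: "The patients may resume at the same dose level when toxicity has resolved to Grade 1 or below or the baseline level", with the proviso "if resolution is achieved within 7 days in the phase 1b part and 14 days in the phase 2 part".

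Table 1, in the column that serves Phase 2, gives recovery levels by toxicity. For Grade 3-4 neutropenia the entry is "Temporary discontinuation until recovery to Grade 2". For Grade 3-4 gastrointestinal and skin toxicity it is "Temporary discontinuation until recovery to Grade 2, or baseline". Grade 3 hepatotoxicity also recovers to Grade 2. The closing row of that column stops treatment permanently if recovery takes more than 14 days, and otherwise restarts it one dose level down. A separate bullet in 9.4 lets any patient who resumes after a temporary hold do so at the dose they were on or one level below it.

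**The concern.** The discretionary bullet has a lower limit on grade but no upper limit, so a Grade 3 or 4 event listed in Table 1 also falls within it. For four toxicity groups the two places then give different recovery levels for the same event. If the bullet is instead confined to Grade 2 events to avoid the overlap, the order is odd: the milder event needs recovery to Grade 1 or baseline, and the more severe one needs only Grade 2.

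The recovery level helps decide who restarts Debio 1347 and when. Investigators who read the section differently would make different restart decisions for like patients. That bears on patient safety, on exposure to the combination, and on the count of patients recorded as stopping Debio 1347 for toxicity. In Phase 2 these are the patients who supply the clinical benefit rate.

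**Working it through.** The plan states no figure to reproduce. The check sets the bullet against the Phase 2 column of Table 1, row by row.

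| Toxicity and grade | Table 1 recovery level | Discretionary bullet | Comparison |
|---|---|---|---|
| Neutropenia, 3-4 | Grade 2 | Grade 1 or baseline | Table looser |
| Gastrointestinal, 3-4 | Grade 2 or baseline | Grade 1 or baseline | Table looser |
| Skin, 3-4 | Grade 2 or baseline | Grade 1 or baseline | Table looser |
| Hepatotoxicity, 3 | Grade 2 | Grade 1 or baseline | Table looser |
| Thrombocytopenia, 4, or 3 with transfusion | Grade 1 | Grade 1 or baseline | Same grade |
| Other non-haematologic, 3 | Grade 1 or baseline | Grade 1 or baseline | Same |
| Febrile neutropenia or neutropenia with infection, 3 | Grade 0 | Grade 1 or baseline | Table stricter |

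Grade 3 hypertension is tied to control rather than a grade, and hyperphosphataemia has its own rules in 9.4.3. The looser level therefore appears in four rows. Where a patient's baseline is already Grade 2, the bullet's baseline alternative is met and the difference disappears.

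Three Phase 2 cases show what the wording does. Baseline is taken as Grade 0 in each.

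1. **Grade 3 diarrhoea, down to Grade 2 on day 14.** Under Table 1 the patient has recovered and restarts one level down. Under the discretionary bullet the condition for resuming at the same dose is not met. Under the separate restart-dose bullet a patient who resumes may do so at the same dose or one level lower, with no recovery grade attached.
2. **Grade 2 diarrhoea, held at discretion, still Grade 2 on day 14.** The gastrointestinal row starts at Grade 3, so Table 1 has no entry. The bullet's condition for the same dose is not met, and the bullet states no consequence. This patient has reached the grade that Table 1 accepts in case 1, but does not meet the bullet's condition.
3. **As case 1, but already reduced to 60 mg.** Table 1 points to a lower level. Section 9.4 requires permanent discontinuation if a dose below 60 mg is needed. The separate restart-dose bullet would allow 60 mg again, and the discretionary bullet would allow it only at Grade 1 or baseline. Recovery level, restart dose and dose floor cannot be read independently here.

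The permanent stop in case 1 depends on what its bullet means by the recovery levels it mentions. That bullet follows the reference to Table 1 and comes before the Grade 1 bullet, and the closing row of Table 1 repeats the 14-day rule. Table 1 is therefore the most natural source, and on that reading the case 1 patient is not stopped for failure to recover. The Grade 1 reading needs the level to be carried from one bullet into another. The missing cross-reference leaves that open.

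**The case against.** The strongest reply is that the two levels belong to different tiers. The Grade 1 sentence is the condition for ending an additional, discretionary hold and resuming at an unchanged dose. The Phase 2 column of Table 1 accepts Grade 2 but then lowers the dose. Fuller recovery for the same dose and lesser recovery for a reduced dose is a coherent scheme, and specific table rows would ordinarily govern the events they list.

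Part of this stands. Grade 1 is not the general restart level of Section 9.4. A restart at Grade 2 does not trigger a compulsory new hold either, because the second hold is optional.

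The tiers are not secured by the text, however. The separate restart-dose bullet offers the same or a lower dose without regard to recovery grade. The DLT-period column of Table 1 lets Grade 3-4 neutropenia and Grade 3 hepatotoxicity recover to Grade 2 and then resume at the same dose. Section 9.2.1 says all Phase 1 patients were off study at the time of the amendment, so that column is evidence of how the section reads rather than a live risk.

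A reader might infer that a patient at Grade 2 on day 14 must either restart or be permanently discontinued, depending on which passage is applied. The documents do not support that as a direct result. The stop most naturally attaches to the Table 1 levels, the discretionary bullet states no permanent stop, and the investigator and PI may discuss resuming after a longer delay.

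A reader might also apply the first-in-human rate of related Grade 3 or higher events in Section 3.3.4 to the Phase 2 maximum: 0.32 × 43 = 13.8, about 14 patients. That does not count patients exposed to this conflict. The 32% covers all related events of that severity, on monotherapy at 10 to 150 mg, and is not limited to the four rows. The share still at Grade 2 on day 14 is not given.

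**Conclusion.** The point holds as an unresolved overlap. In four Phase 2 rows of Table 1 the accepted recovery level is Grade 2, while a bullet whose scope literally includes the same events ties same-dose resumption to Grade 1 or baseline. No precedence rule is given, and a hold for a Grade 2 event can require fuller recovery than a hold for a Grade 3 event of the same type. The 14-day stop rule lacks the cross-reference that would settle its own meaning, so permanent discontinuation at Grade 2 on day 14 is a possible reading and no more.

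The number of patients affected cannot be derived from the documents. The conflict is not remote: Section 3.3.4 names cutaneous toxicity as a main reason for dose modification, and skin is one of the four rows. The other main reason, hyperphosphataemia, lies outside them. The effect on the primary endpoint is indirect, because Section 9.4 lets patients who stop Debio 1347 purely for toxicity stay on study with fulvestrant. What may shift is exposure to the combination and the reported toxicity discontinuations. The conclusion rests on reading the bullet's grade range literally; its limitation to additional, discretionary holds has been taken into account.

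**What to change.** Reconcile the Section 9.4 bullets with Table 1 in one wording amendment that states:

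- which events the discretionary-hold bullet covers;
- which recovery level the 7- and 14-day permanent-stop rule refers to for each toxicity, with an explicit cross-reference;
- how that level relates to the three restart-dose statements (the discretionary bullet, the separate restart-dose bullet and the closing row of Table 1), including for a patient already at 60 mg.

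The clinical team decides the thresholds and which statement governs; this review proposes none. The cost is a protocol wording amendment, with no added visits, assessments or analyses.

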4.1 OVERVIEW OF STUDY DESIGN/INTERVENTION

4.2 Design

This is an open-label, single institution, phase Ib/phase II non-randomized trial that evaluates the safety, tolerability and anti-tumor activity of fulvestrant and Debio 1347 in patients with ER+/HER2- metastatic breast cancer (MBC) that are FGFR-amplified (as confirmed by a CLIA certified laboratory).

The phase I portion of this trial will have 2 dose levels: dose level 1 (80mg) and a de-escalation level (60mg) if the 80mg dose level has intolerable toxicities (N= minimum 4 and maximum 12). Fulvestrant will be administered intramuscularly at standard doses (500 mg loading dose on days 1, 14, and 28 of the first month, then maintenance dosing every 28 days, ± 3 days) with no dose-escalation. Only the dose of Debio 1347 will be de-escalated as shown below. There will be no intra-patient dose escalation. 1 cycle = 28 days.

The Dose Limiting Toxicity (DLT) observation period includes Day 1 to Day 28 of Cycle 1, plus the assessments prior to drug administration on Cycle 2, Day1.

Cohort/Dose level	Debio 1347	Fulvestrant
-1	60mg	500mg IM
1 (Starting dose cohort)	80mg	500mg IM

If none *or* one of the initial 3 patients in dose level 1 has DLT, 3 additional patients will be treated at the same dose level. If 2 or more patients experience DLT at this dose level, then dose level -1 will be evaluated. Should 2 or more patients experience DLT at dose level -1, the study will stop accrual. If only 1 of the 3 initial patients experiences a DLT at dose level -1, 3

additional patients will be evaluated at this dose level. Patients who withdraw before completing a full cycle of treatment for reasons other than development of a DLT will be replaced.

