9.4.2 Hyperphosphatemia (Phase I)

1. Initial Modifications on Treatment:

Serum phosphorus level	
5.5 – 6.9 mg/dL	
 1. Continue Debio 1347 2. Continue (or increase) sevelamer powder 2400mg TID 3. Add Fosrenol 1g TID 4. Recheck within 7 days

≥ 7 mg/dL	
 1. Hold Debio 1347 2. Continue (or increase) sevelamer powder 2400mg TID 3. Add Fosrenol 1g TID 4. check within 7 days -> resume if Ph < 5.5 and recheck within 7 days of resumption
----------------	---

*If sevelamer is not available or tolerable, alternate phosphate reducing agents or preparations can be utilized.

2. Second Modification on Treatment

Serum phosphorus level	
5.5 – 6.5 mg/dL	
 1. Cont Debio 1347 2. Cont sevelamer powder to 2400mg TID increase Fosrenol to 1.5mg TID 3. recheck within 7 days
6.6-6.9mg/dL	
 1. Cont Debio 1347 2. Cont sevelamer powder to 2400mg TID 3. Cont Fosrenol 1g TID 4. add acetazolamide 250mg BID 5. recheck within 7 days
≥ 7 mg/dL	
 1. Hold Debio 1347 – consider dose reduction 2. Cont sevelamer powder to 2400mg TID 3. increase Fosrenol to 1.5g TID 4. add acetazolamide 250mg BID 5. check within 7 days -> resume if Ph < 5.5

*If sevelamer is not available or tolerable, alternate phosphate reducing agents or preparations can be utilized.

3. Subsequent Modifications:

Serum phosphorus level	
> 5.5 mg/dL-6.9mg/dL	
 1. If not already, maximize regimen to include: sevelamer powder to 2400mg TID fosrenol to 1.5g TID acetazolamide 250mg BID 2. If already maximized, consider dose reduction (without interrupting drug) 3. Recheck within 7 days
≥ 7 mg/dL	
 1. Hold Debio 1347 – dose reduction needed 2. Maximize regimen to include: sevelamer powder to 2400mg TID fosrenol to 1.5g TID acetazolamide 250mg BID

	3. check within 7days -> resume with dose reduction if Ph < 5.5
--	---

*If sevelamer is not available or tolerable, alternate phosphate reducing agents or preparations can be utilized.

- For patients whose phosphorous control improves after Debio 1347 dose reductions, escalation of the phosphorus regimen can be considered at the discretion of the investigator. Subsequent to any such adjustment, phosphorous level should be rechecked within 7 days.

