12.3.2 MTD/RP2D Determination Population during Phase 1b portion

The population evaluable for MTD/RP2D determination will consist of all patients who received at least 75% of the planned Debio 1347 dose during the DLT period (Day 1 to Day 28 of Cycle 1 and assessments prior to drug administration on C2D1). Patients who experienced a DLT will be included in the MTD/RP2D determination population regardless of the dose of Debio 1347 received.

Patients who fulfill any of the following situations will be excluded from the MTD/RP2D determination population:

1. Administration during the DLT period of non-permitted concomitant treatments with impact on DLT evaluation.
2. Proper DLT/safety evaluation is judged to be difficult because of protocol violation(s).

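### Section 9.4 limits dose reduction to phase 2 while other passages allow it in phase 1b, and because 60 mg is exactly 75% of 80 mg, a patient reduced in Cycle 1 can still count as evaluable and DLT-free at 80 mg

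*Combined protocol and SAP*

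**What the plan says.** The documents disagree on whether Debio 1347 may be reduced in phase 1b.

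- **Section 9.4, text.** One bullet confines reduction to phase 2: "Only in the phase 2 portion, one dose reduction can be undertaken except for dose level -1 (60mg". Another bullet in the same list presupposes it in phase 1: "Patients will be permanently discontinued if reduction beyond <60mg/day is necessary in both phase 1 and phase 2 portions of the study".
- **Section 9.4, Table 1, recovery row.** In the column for the phase I DLT period, the default after recovery within 7 days is the same dose, and the cell then adds: "Dose reduction during the DLT has to be discussed with the PI". The next column, shared by phase 2 and by phase I after the DLT period, gives retreatment one level lower.
- **Section 9.4.2, headed Phase I.** At phosphate up to 6.9 mg/dL, once the phosphate-lowering regimen is at its maximum, the investigator is told to "consider dose reduction (without interrupting drug". At 7 mg/dL or more the drug is held. Reduction is then to be considered at the second step and is needed at later steps.

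Section 12.3.2 makes a patient evaluable for the MTD/RP2D if he or she "received at least 75% of the planned Debio 1347 dose during the DLT period". It adds: "Patients who experienced a DLT will be included in the MTD/RP2D determination population regardless of the dose of Debio 1347 received". It does not define planned dose or say how a dose-reduced patient is classified. Under 9.5, patients who do not qualify are replaced.

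Section 9.3 does not list dose reduction as a DLT. The nearest items are a treatment delay of more than 7 days and any event that the investigator judges intolerable.

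Under 4.2 and 14.0, 80 mg is retained if fewer than two of six patients have a DLT. Section 9.1 (Treatment/Intervention Plan) names 80 mg daily for phase 2, and 9.2.1 records that all phase 1 patients were already off study.

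**The concern.** Phase 1b asks whether 80 mg with fulvestrant can be tolerated for one cycle. A minimum-exposure rule is there so that a patient recorded as DLT-free has had enough drug at the assigned level for that record to mean something. Here the only lower dose level sits exactly on the limit, and the limit is inclusive. If reduction inside the DLT window is possible, a patient can spend much of Cycle 1 at 60 mg and still enter the 80 mg denominator as DLT-free.

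With six patients and at most one DLT allowed, each patient is one sixth of the evidence for the dose given to up to 43 phase 2 patients. The contradiction also means that the documents alone do not tell a reader whether such patients could exist.

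**Working it through.** The plan gives no derived figure to reproduce; 75% is a fixed threshold.

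**Inputs**
- Dose levels from 4.2: "dose level 1 (80mg) and a de-escalation level (60mg) if the 80mg dose level has intolerable toxicities".
- Window from 4.2: "1 cycle = 28 days", so 28 dosing days.
- Threshold from 12.3.2: at least 75%, inclusive.
- Assumption: planned dose means the assigned level on every day, counted in milligrams.

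**Threshold**
- Planned: 28 × 80 = 2240 mg.
- 75% of planned: 0.75 × 2240 = 1680 mg.
- All days at 60 mg: 28 × 60 = 1680 mg, which is exactly 75%.

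**General rule.** Let a be the days at 80 mg, followed by h hold days, with the remaining days at 60 mg.
- Dose received = 80a + 60(28 − a − h) = 1680 + 20a − 60h.
- This is at least 1680 if and only if a ≥ 3h.

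With no hold (h = 0) the condition always holds. After a hold it depends on timing:

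| Full days | Hold | Days at 60 mg | Received (mg) | Share of 2240 | Evaluable on dose |
|---|---|---|---|---|---|
| 21 | 0 | 7 | 2100 | 93.75% | yes |
| 14 | 4 | 10 | 1720 | 76.8% | yes |
| 14 | 5 | 9 | 1660 | 74.1% | no |
| 7 | 3 | 18 | 1640 | 73.2% | no |

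**Can the protocol's own rules lead to an evaluable row?** Take phosphate of 5.5 to 6.9 mg/dL on day 8 and at least 7 mg/dL on day 15, both scheduled chemistry days. The second step of 9.4.2 then holds the drug and raises dose reduction. Suppose the level never exceeds 9.0 mg/dL and is below 5.5 mg/dL after four days, and dosing resumes at 60 mg.
- The hyperphosphataemia items in 9.3 are not met. The first needs more than 7 consecutive days above 7.0 mg/dL, and the others need values above 9.0 or 10.0 mg/dL.
- A 4-day hold is shorter than the delay item of more than 7 days.
- Received dose is 14 × 80 + 10 × 60 = 1720 mg, or 76.8%.

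Unless another DLT item applies, or the investigator calls the event intolerable, this patient is evaluable and DLT-free at 80 mg.

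**Same patient, other reading.** If the 75% means doses taken at the assigned level, the figure is 14/28 = 50%. The patient is not evaluable and would be replaced under 9.5. The classification turns on a term that 12.3.2 leaves undefined.

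**The case against.** **The Table 1 sentence may cover only patients who already had a DLT.** Sections 9.3 and 9.4 both let such patients continue after an adjustment, and 9.4 requires discussion with the PI. Read that way, the reduced patient is counted as a DLT under 12.3.2 and nothing is hidden. This is a fair reading of that sentence. It does not reach 9.4.2, which is keyed to phosphate rather than to a DLT, and it leaves the contradiction within 9.4.

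**The result is not automatic.** A reader might infer that any patient cut to 60 mg in Cycle 1 counts as a clean 80 mg patient. The documents do not support that. The Table 1 row follows a hold, its default is the same dose, and a patient with fewer than three full-dose days per hold day falls below 75%. Many triggering toxicities are DLTs themselves or lead to permanent discontinuation.

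**The no-hold route is normally late.** In 9.4.2 it requires a regimen already at its maximum. On the 5.5 to 6.9 mg/dL path neither of the first two steps reaches that, so the third abnormal result maximizes the regimen and the fourth raises reduction. With abnormal results on days 4, 8, 15 and 22, that is day 22. By then 21 × 80 = 1680 mg has already been taken, so the 60/80 coincidence is irrelevant. Rechecks are due within 7 days and could come sooner, but very early no-hold reductions have no explicit route.

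**Counting a patient below the DLT thresholds as DLT-free follows the definition.** This stands. The issue is evaluability at 80 mg, not whether a reduction ought to be a DLT.

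**80 mg has other support.** Sections 3.3.4 and 3.4.1 report it as the MTD and recommended dose from a 57-patient first-in-human escalation. This also stands, and it limits what is at stake.

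**Conclusion.** The concern holds in a limited form. Section 9.4 conflicts with 9.4.2, with Table 1 (certainly in the column shared with phase 2, and in the DLT-period column on its plainer reading) and with one of its own bullets. Separately, the 75% limit read in milligrams cannot exclude a patient reduced to 60 mg without a hold. After a hold it excludes only those with a < 3h. The worked route gives 76.8% in milligrams against 50% in doses at the assigned level.

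This rests on planned dose meaning the assigned level for 28 days, and on the triggering event not being a DLT.

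A reader might go further and infer that the 80 mg RP2D was in fact reached with such patients. No document shows that any phase 1b patient was reduced in Cycle 1. Nor can a probability be put on it. The 49% with dose modification in the first-in-human trial (3.3.4) covers all modifications, at doses from 10 to 150 mg, and is not limited to Cycle 1. It is not a rate of Cycle 1 reductions at 80 mg.

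**What to change.** 1. **Reconcile** the 9.4 text, both phase I columns of Table 1 and 9.4.2 on whether phase 1b dose reduction is permitted, and clarify whether the Table 1 sentence means the DLT period or patients who have had a DLT. Which clinical rule applies is for the sponsor and investigator.
2. **Define the 75% in 12.3.2** as doses taken at the assigned dose level. A no-hold reduction from day 22 onward would still qualify (21/28 = 75%), so the report in item 3 is needed as well.
3. **Report from the dosing records**, since phase 1b is complete, whether any patient counted at 80 mg was reduced in Cycle 1, the day and length of any hold, and how the patient was classified. Give the RP2D basis (DLTs/evaluable) with and without such patients. As the definition would be changed after the fact, show both results and do not replace one with the other.

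No new DLT rule is needed or proposed.

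The cost is protocol wording and a re-tabulation of Cycle 1 dosing for at most 12 patients. The downside is that the stated support for 80 mg may become slightly less favourable. If no counted patient was reduced, one sentence saying so closes the point.
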